1. INTRODUCTION

The success of total knee arthroplasty (TKA) depends on a multitude of surgical factors, including appropriate rotational alignment of the prosthetic components [11]. Despite the high success rate of TKA, early post-operative complications can occur as a result of poor rotational positioning of one or both components [5, 8, 18], which may ultimately require revision surgery [11, 13]. Complications indicative of tibiofemoral rotational incongruity may present early in the post-operative period with patient complaints of anterior knee pain, joint stiffness, the sensation of instability, and difficulty navigating stairs and inclined planes. It has been reported that the incidence of anterior knee pain may be as high as 20% after a TKA [1, 10, 14]. Clinical examinations of these incongruent patients can reveal restricted range of motion, patellar crepitus, patellar maltracking (tilt - dislocation), and significant rotational mismatch displayed by rotational gait disturbances (foot progression angle) [3, 4, 6, 14, 16-18]. Suboptimal outcomes due to incongruity, which have been well documented in literature, may be associated with only small rotational deviations of the tibial and femoral components. For instance, Barrack, et al. reported that as little as 6.2° of internal rotation (IR) of the tibial component is associated with postoperative anterior knee pain [1]. Berger, et al. showed that combined IR of the tibial and femoral components from 3° to 8° was correlated with patellar subluxation, and 7° to 17° of combined IR correlated with observed patellar dislocation or patellar prosthesis failure [2].

While there are advocated methods for establishing optimal rotation of the femoral component, no such reliable method currently exists for positioning the tibial tray [12]. Thus, surgeons must rely upon anatomic landmarks to guide proper tibial component orientation. These landmarks include: the projected femoral transepicondylar axis, medial third of the tibia, posterior condylar line of the tibia, mid-sulcus of the tibia spine, malleolar axis, patellar tendon, and axis of the second metatarsal [12]. However, difficulty may exist in identifying these landmarks during surgery. Poor intraoperative visibility, coupled with variations in patient anatomy, can contribute to unfavorable positioning. It has been suggested that aligning the tibial tray to the mid-third of the tibial tubercle may reduce positioning outliers with more consistency than referencing other anatomic landmarks [15]. Yet, reliance on these landmarks is still subject to variability [12, 19] and may not provide the precision necessary to avoid complications, such as those described by studies conducted by Barrack, et al. and Berger, et al. As such, an obvious need exists to refine clinical technique, and to explore new methods to optimize tibiofemoral implant congruency.

Recently, technology has made it possible to embed microelectronics into the standard tibial trial [9] (VERASENSE™ Knee System, OrthoSensor, Dania FL). This array of sensors provides dynamic intraoperative feedback regarding tibiofemoral position and quantitative pressure at peak contact points in the medial and lateral

compartments during TKA trailing. Utilizing sensor-derived data, the surgeon can now evaluate intercompartmental loading throughout the range of motion and correct for soft-tissue abnormalities while receiving real-time feedback regarding joint position and the tibiofemoral relationship defined by the contact point location.

2. STUDY DESIGN

The study is designed as a prospective, randomized (two-cohort) double-blinded clinical evaluation and will be conducted at multiple centers throughout the United States. Approximately 500 patients will be included and followed for a period of 2 years. Clinical Assessments will be performed at baseline, 6 weeks, 6 months, 1 and 2 years after surgery.

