5. METHODS / PROCEDURES

Patients indicated for TKA and who meet all study eligibility criteria will be asked to participate in the study. Eligible patients will receive a primary unilateral PCL-retaining or – sacrificing TKA using the Stryker Triathlon Total Knee System *with* or *without* the use of the VERASENSE™ Knee System. Patients will be enrolled in a consecutive series consisting of two cohorts (Groups A and B). Both groups are described below:

Group A – Control (Surgeon-Guided) will consist of **250** consecutive patients who will undergo primary unilateral PCL-retaining or – sacrificing TKA using the Stryker Triathlon Total Knee System *without* the use of VERASENSE to guide rotational alignment and balance. **Prior to closing the arthrotomy, VERASENSE will be utilized in a surgeon-blinded fashion to record rotational alignment and intercompartmental pressures through a range of motion.**

Group B (Sensor-Guided) will consist of **250** consecutive patients who will undergo primary unilateral PCL-retaining or – sacrificing TKA using the Stryker Triathlon Total Knee System *with* the use of VERASENSE to guide rotational alignment and balance. The sensor data will be used for balancing per the VERASENSE protocol below.

Each patient will be given a unique study number once informed consent has been obtained. The investigator will be blinded to the patient study number and the patient will be blinded to his/her assigned group. It will be important that all patients remain blinded to their assigned group. The patient will be informed during the consent process that they may or may not receive their knee replacement procedure using the VERASENSE Knee System.

Radiographic outcomes will be assessed on all patients within the first 12 weeks and at the annual visits. Any postop complications will also be monitored.

Surgical Protocol – Using VERASENSE

All knees will be prepared using standard instrumentation and a measured resection or gap balancing technique. The following steps will be performed when using VERASENSE:

Step 1: Establish Tibial Tray Rotation:

Select and position appropriate sized trial tibial tray. Align the tray to the anatomy (mid-medial third of the tubercle) as recommended by the manufacturer's surgical technique. Insert a single anterior or posterior pin (medially or laterally) into the trial tray to allow for internal / external rotational adjustment while maintaining optimal medial / lateral coverage.

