Once tibial tray rotation has been assessed, the medial and lateral compartment pressures will be evaluated in the coronal and sagittal planes. The soft tissue gaps will be evaluated and recorded at **10°**, **45°**, and **90°** of flexion, with the hip in neutral rotation and the femur supported just proximal of to the knee. The capsule must be closed provisionally during assessment at each pose using a towel clip placed above and below the patella in the medial retinaculum. Incremental balancing using a pie-crusting technique with an 18-gauge needle or #11blade scalpel is recommended to address ligamentous tension when necessary. Additional bony resections may be necessary for excessive loading (refer to surgical reference guide). Previous research evaluating the use of VERASENSE during TKA suggests a load differential of up to 15 lbs or less between the medial and lateral condyles is indicative of soft-tissue balance [7] (Figure 7). These balancing parameters will be the target in the sensor-guided group.

Figure 7 – Left: The mediolateral intercompartmental difference, pre-release, is 42 lbs. This value exceeds the 15 lb. limit, thus classifying this joint as “unbalanced.” **Right:** The mediolateral intercompartmental difference, post-release, is 1 lb. and was classified as “balanced” upon closing.

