- Radiographic evaluation via Mediolateral and anteroposterior x-rays as is standard of care. The prevalence and location of radiolucency and/or osteolysis is evaluated on both AP and lateral views at each patient’s routine postoperative

follow-up visits. These evaluations are performed by each patient's operating surgeon.

- Complications, adverse events, and survivorship data will be collected and reported. This information will be gathered at each of the study follow-up visits.

c. Data Collection Periods:

Data will be collected pre-operatively, intra-operatively, and post-operatively at 6 weeks, 6 months, and 1 year. All time point windows are determined using the date of surgery (DOS) as day 0, including all annual visits. The visit windows are as follows:

Pre-operative: within 3 months prior to the date of the surgery excluding

*Pre-operative radiographs. Pre-operative radiographs taken within 12 months of scheduled knee replacement surgery are sufficient.

Intra-operative: within 2 weeks after the date of surgery

6 weeks: DOS + 6 weeks ± 4 weeks

6 months: DOS + 6 months ± 45 days

1 year: DOS + 1 year ± 90 days

2 year: DOS + 2 year ± 90 days

Table 1. Schedule of study assessments

Data Collected	Pre-op Baseline	Operative Discharge	6 Weeks	6 Months	1 Year	2 Years
Obtain Written Informed Consent	X					
Demographics	X					
Intra Operative		X				
EQ-5D	X		X	X	X	X
New-KSS	X		X	X	X	X
FJS			X	X	X	X
Knee Pain Evaluation Form				X	X	X
Radiographic Alignment	X		X	X	X	X
Adverse Event Reporting (When Present)		(X)	(X)	(X)	(X)	(X)

10. Analysis to be Performed on Data (e.g. Statistical Analysis)

Analysis of the data will be performed using SPSS version 21. Comparative Statistics will be run between outcomes data stratified by both groups: Analysis of variance (AVOVA) will be used to assess the difference between each group, with post-hoc t-tests to demonstrate significance. Separate analyses will be performed to evaluate power of sample sizes and any correlative affect that demographic/clinical variables may have on patient outcomes.

11. Monitoring of data collection

The Sponsor will monitor all data collected for accuracy and completion. The site will be monitored at least once per calendar year following the initial/first-monitoring visit.

12. Patient Identification

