Each patient who signs an informed consent document will be given a unique, sequential 3-digit number. The three initials of each patient will be used (first, middle, last). In the case where the subject does not have a middle initial, that placeholder will be held by a dashed line (-). This unique patient identifier will be used on all study-related documentation for each subject enrolled in the study. The patient's initials will be used to further identify the subject; no names will be used.

13. Screening Enrollment Logs

A record of all patients consented for the study, with their consecutively assigned study numbers, will be maintained in the site's Regulatory Binder. This log will be identified as the Screening/Enrollment Log. Patients who sign a consent form but who do not continue into the study for whatever reason (i.e., cancel surgery) will be assigned a unique subject identifier which **WILL NOT BE REASSIGNED** to anyone else.

14. Patient Identification

Each patient who signs an informed consent document will be given a unique, sequential 3-digit number. The three initials of each patient will be used (first, middle, last). In the case where the subject does not have a middle initial, that placeholder will be held by a dashed line (-). This unique patient identifier will be used on all study-related documentation for each subject enrolled in the study. The patient's initials will be used to further identify the subject; no names will be used.

Example: Subject number: 001.

Subject initials: FML where F = first initial, M = middle initial, L = last initial. This subject's unique identifier would be 001 and uniquely associated with the initials FML.

15. Institutional Review Board Approval and the Informed Consent Document.

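### The trial is called double-blinded, but only the patient is blinded to group; the operating surgeon knows the arm and reads the films, and no blinding is stated for the clinicians who score the knee and record pain

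*Combined protocol and SAP*

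**What the plan says.** Section 2 gives the label: "The study is designed as a prospective, randomized (two-cohort) double-blinded clinical evaluation". It does not name the two blinded parties.

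Section 5 does: "The investigator will be blinded to the patient study number and the patient will be blinded to his/her assigned group". The sentence that follows stresses keeping patients blinded and mentions nobody else. For Group A, Section 5 adds that before closure "VERASENSE will be utilized in a surgeon-blinded fashion to record rotational alignment and intercompartmental pressures". For Group B, Step 4 sets a load-difference limit between the compartments and says: "These balancing parameters will be the target in the sensor-guided group".

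Sections 12 and 13 describe the study number. "Each patient who signs an informed consent document will be given a unique, sequential 3-digit number". "This unique patient identifier will be used on all study-related documentation for each subject enrolled in the study". The site's own log lists all consented patients "with their consecutively assigned study numbers, will be maintained in the" regulatory binder.

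Section 9 says who records outcomes:

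- **Radiographs** (radiolucency and osteolysis): "These evaluations are performed by each patient's operating surgeon".
- **KSS:** the objective part is described as surgeon-completed and includes a pain VAS. Patients record satisfaction, function and expectations.
- **Knee Pain Evaluation Form:** completed by the investigator, where it applies.
- **EQ-5D and FJS:** patient-reported.

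**The concern.** A reader of Section 2 will take it that the people who score outcomes do not know the arm. Section 5 does not provide for that. Less post-operative knee pain is named in objective 2 and in the hypothesis, yet the only form dedicated to knee pain is filled in by an assessor with no stated blinding to arm, and a pain VAS sits in the part of the KSS attributed to the surgeon.

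If an assessor who knows the arm expects sensor guidance to help, a between-arm difference on these items could reflect that expectation and still be reported as double-blinded evidence. The exposed part is the clinician-completed portion of objective 2. The supplied text names no primary endpoint, so it does not settle whether the main conclusion will rest on these items.

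**Working it through.** The plan gives no figure to reproduce on this point. The check is a comparison of the text, followed by a count of records.

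**Who is blinded to group**

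1. *Patient.* Yes, stated in Section 5.
2. *Operating surgeon.* No. Under Section 4 the intervention is the surgeon's own use of the sensor. In Group B the surgeon balances to the displayed readings; in Group A the surgeon works without them. The surgeon-blinded recording in Group A hides the readings, not the arm.
3. *Investigator.* Not stated. One sentence in Section 5 uses both terms, group for the patient and study number for the investigator, so they cannot be read as the same thing. The number is issued in sequence at consent, and no link between number and arm is described. It also goes on every study document and into a log held at the site, so an investigator could hardly avoid seeing it. If blinding to group was meant, the text does not say so.
4. *Independent assessor or film reader.* None is described in the supplied text.

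**What follows for each outcome**

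| Outcome | Recorded by | Blinded to arm? |
|---|---|---|
| Radiolucency, osteolysis | Operating surgeon | No |
| KSS objective score | Surgeon (not specified as the operating one) | Not stated |
| Knee Pain Evaluation Form | Investigator (not specified as the operating surgeon) | Not stated |
| KSS patient items, EQ-5D, FJS | Patient | Yes |

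**How many records are involved**

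Inputs are the post-operative visits in Table 1: EQ-5D 4, KSS 4, FJS 4, pain form 3, radiographs 4.

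- Total per patient: 4 + 4 + 4 + 3 + 4 = 19.
- Wholly or partly clinician-completed: KSS 4 + pain form 3 + radiographs 4 = 11; 11/19 = 57.9%.
- Wholly patient-completed: EQ-5D 4 + FJS 4 = 8; 8/19 = 42.1%.
- Section 5 schedules radiographs only three times (first 12 weeks, 1 year, 2 years). On that schedule the share is 10/18 = 55.6%.
- If the KSS is split into its clinician and patient parts, there are 19 + 4 = 23 records: 11 clinician (47.8%) and 12 patient (52.2%).

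Maximum numbers of records across the trial:

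| Record | 500 patients, full follow-up | 400 patients (assumed 20% loss) |
|---|---|---|
| Radiographic readings, Table 1 | 4 × 500 = 2,000 | 4 × 400 = 1,600 |
| Radiographic readings, Section 5 | 3 × 500 = 1,500 | 3 × 400 = 1,200 |
| KSS objective scores | 4 × 500 = 2,000 | 4 × 400 = 1,600 |
| Pain forms (fewer if completed only where applicable) | 3 × 500 = 1,500 | 3 × 400 = 1,200 |

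The protocol states no expected loss; the 20% is an assumption for illustration.

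**The case against.** The strongest reply accepts that the label is wrong but disputes how much hangs on it.

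- **Surgeons cannot be blinded in such a trial.** True, and nobody need ask for it. The label still has to match the design.
- **The 58% depends on the counting rule.** It does. Counting the two parts of the KSS separately brings the clinician share to 48%. The 58% is right only as a count of forms wholly or partly completed by a clinician, and neither figure measures bias.
- **The radiograph row in Table 1 is headed alignment, while the sentence about the operating surgeon follows the text on radiolucency and osteolysis.** This stands as a caution. Section 9 does place the radiolucency evaluation at routine follow-up visits, but the text leaves open whether the surgeon also measures alignment. The radiographic totals are therefore upper limits.
- **The KSS sentence describes the instrument in general, and the case report forms are not supplied.** This also stands. The VAS may already be the patient's own rating, and the pain-form investigator may not have operated. What is missing is any statement that either assessor is blinded.
- **Pain is also covered by patient-reported measures.** Section 9 says so. This limits the damage and supports resting pain claims on patient entries.
- **The study-number sentence may be a garbled attempt to blind the investigator to group.** Possibly. It then needs correcting, and the operating surgeon would still know the arm.

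**Conclusion.** The concern holds. The plan claims double-blinding, and its own text provides blinding to group for the patient alone. The radiolucency and osteolysis readings are explicitly made by a surgeon who knows the arm. For the KSS objective score and the pain form, the finding is that no blinding is stated; it is not established that their assessors know the arm.

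The exposure is 11 of 19 scheduled post-operative records per patient on the wholly-or-partly count (10 of 18 on the Section 5 radiograph schedule; 11 of 23 with the KSS split). No bias size can be derived from the documents and none is claimed.

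This should be fixed, but it does not undo the trial. EQ-5D, FJS and the patient-recorded KSS items stay protected as long as patient blinding holds, and the sensor readings for objective 1 are not affected. The conclusion rests on the supplied text; the case report forms were not available.

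**What to change.** 1. In Section 2, describe the trial as patient-blinded (surgeon not blinded). That wording stays true even if another assessor is later named as blinded. In Section 5, correct the study-number sentence so that it says who, other than the patient, is unaware of group.
2. At visits already scheduled, have the patient enter the KSS pain VAS ratings and the presence and location of pain before seeing the surgeon. Leave the examination items with the clinician. Base between-arm pain claims on these entries and the patient-reported measures. If the VAS is already the patient's own rating, say so and leave that item unchanged.
3. Report the clinician-scored KSS items and the radiographic readings as unblinded, supportive data.

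**Cost.** Protocol wording, a patient-entry part on two forms, and a few minutes of patient time at existing visits. No extra staff, visits or readers.

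**Downsides.** The double-blinded label is lost. The way some pain items are completed changes slightly, including within the KSS, which Section 9 describes as validated. The KSS examination items and the film readings remain unblinded.

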3. OBJECTIVES

The objectives of the study are twofold: 1) Evaluate how intra-operative sensing may assist the surgeon with tibiofemoral rotational alignment by testing the precision and variability of setting tray rotation to the mid-third of the tibial tubercle. 2) Understand if patients with a combined axial rotation couple at the tibiofemoral joint and quantitative intercompartmental balance, achieved with the use of VERASENSE, exhibit less post-operative knee pain and improved clinical outcomes. Radiographic outcomes will also be assessed to measure post-operative alignment and to evaluate the prevalence and location of radiolucency and/or osteolysis.

Hypothesis: TKA with VERASENSE results in a more reliable and precise option for establishing implant-to-implant congruency and joint balance leading to less knee pain, faster return to normal activities and higher patient satisfaction compared to TKA without VERASENSE.

The secondary objectives of the study are to establish correlations between the intraoperative VERASENSE data, the surgeon's perception of balance and patient outcomes in addition to understanding any learning curve associated with using new technology.

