4. TREATMENT AND DEVICE

The intervention involves the use of VERASENSE by the surgeon during Total Knee Replacement Surgery. VERASENSE is available for use with the Stryker Triathlon Total Knee System. VERASENSE replaces the standard tibial trial inserts and is embedded with microelectronics and sensors to provide surgeons with real-time knee kinetic data. The data is wirelessly transmitted to a graphic display (VERASENSE Knee Application), allowing surgeons to quantify and assess soft tissue intercompartmental loads throughout the range of motion. The VERASENSE sensor is not an investigational device. OrthoSensor, Inc., received FDA 510K clearance in 2009. The indication for use is a tool for adjustment of the femoral knee

implant to reduce instability from flexion gap asymmetry. The VERASENSE sensor is sterile and single patient use.

4.1 – Description of VERASENSE

- One articulation (Figure 1): Cruciate Retaining (CR); However can be utilized with Posterior stabilizing implant designs
- Six Sizes: 2, 3, 4, 5, 6, 7
- Four attachable shim thicknesses: 9, 11, 13, and 16mm

[figure not shown]
Figure 1 – CR VERASENSE Inserts

4.2 – VERASENSE Knee Application (Figure 2)

- Graphic display is a 27" iMac with keyboard, mouse, bar-code reader, activation magnet, receiver (Antenna)
- Software application provides femoral contact point location and load values for medial and lateral condyles; kinematic tracking; tray rotation, tibia varus/valgus axis; mechanical axis

Figure 2 – Graphic Display

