Figure 2 - view of proximal tibia referencing the mid-medial third of tibial tubercle

Step 2: Sensor Insertion

Insert the VERASENSE Sensor with appropriate sized shim attached to replicate thickness of standard trial insert. In a tight knee capsule, it may be necessary to insert the VERASENSE Sensor prior to insertion of the femoral trial. DO NOT utilize excessive force or impact the sensor directly with a mallet.

Figure 3 - VERASENSE™ Sensor activated and inserted into knee

Step 3: Establish Tibial Tray Rotation Utilizing Contact Points

With the leg supported in 10° flexion, rotate the tibial tray to the most posterior contact point (internally or externally) as needed to horizontally align the medial and lateral contact points within 5° of each other. Reference protocol found in Appendix I on how to hold the leg using VERASENSE. A positive (+) value in the Contact Point Rotation (CP Rotation box) indicates internal rotation (IR); a negative (-) value indicates external rotation (ER). Figures 4-6.

When preferred tray rotation is achieved (within 5° Contact Point Rotation):

- Add additional Pin to stabilize tray
- Flex knee and confirm patellar tracking
- Record the final value

[figure not shown]

Figure 4 - VERASENSE™ Sensor as displayed on graphical user interface. CP (Contact Point) Rotation degree [in red box] references the degree of tibiofemoral incongruity. Yellow circles correspond to femoral contact points. The number 8 represents total pounds of pressure in the medial and lateral compartments

Figure 5 - Left: Medial and lateral femoral contact points (indicated by arrows) demonstrate tibiofemoral rotational incongruity, due to excessive IR of the tibial tray. Right: After correcting for IR, the femoral contact points demonstrate symmetry (indicated by arrows).

Figure 6 - Left: Example of excessive ER (indicated by arrows), as a result of referencing the mid-third of the tibial tubercle, shown by the sensor interface. Middle: Trial tibial/femoral components in place with the sensor; tibial tray visually and digitally exhibiting external rotation. Right: The tibial tray is rotated to improve congruity, as seen by the parallel contact points (indicated by arrows) on the sensor interface.

Step 4: Balance Soft-Tissue Sleeve

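### Objective 1 asks about the precision of tray rotation, but no rotation outcome or measure of spread is designated, the named tests compare means, and the two arms' stated readings come from different stages of surgery

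*Combined protocol and SAP*

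**What the plan says.** Section 3 gives the first objective as "testing the precision and variability of setting tray rotation to the mid-third of the tibial tubercle", and the hypothesis is that sensor guidance is a "more reliable and precise option for establishing implant-to-implant congruency".

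Section 10 is the whole analysis plan. It says "Comparative Statistics will be run between outcomes data stratified by both groups", and then "Analysis of variance (AVOVA) will be used to assess the difference between each group, with post-hoc t-tests to demonstrate significance". It adds unspecified analyses of power and of correlation with demographic and clinical variables. It names no SD, variance, outlier proportion or test of spread. The operative data list in Section 9 has no rotation item. Table 1 has only a general intra-operative row and a radiographic alignment row.

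Rotation does appear elsewhere:

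- Section 4.2 lists among the software outputs "kinematic tracking; tray rotation, tibia varus/valgus axis; mechanical axis".
- Section 5, Step 3 (the sensor-guided procedure) uses Contact Point (CP) Rotation, in degrees, positive for internal and negative for external. The position is given as "With the leg supported in 10° flexion". The final value is recorded once it is within 5°, and Step 4 (soft-tissue balancing, with possible bone resection) follows.
- Section 5, Group A: "Prior to closing the arthrotomy, VERASENSE will be utilized in a surgeon-blinded fashion to record rotational alignment", together with compartment pressures through a range of motion. No output and no reading angle are named.

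**The concern.** A t-test or ANOVA on a signed angle asks whether the arms have the same average. Precision concerns how widely values scatter, and internal and external errors of equal size cancel in a mean. As written, the plan could return a null when precision improved, or a significant result when only the average moved. The choices that decide this (which output, signed or absolute, which angle) are left open and could be made after the data are seen.

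The quantity is also unsettled. Figure 4 describes CP Rotation as a reading of tibiofemoral incongruity. That fits the hypothesis, but it is not the same as deviation from the tibial tubercle, which Objective 1 names. Group A's rotational alignment is tied neither to CP Rotation nor to the software's tray rotation.

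Finally, Group B's Step 3 value is taken when it has just met its own 5° target. Setting it against Group A's closing value credits Group B with that target, whether or not it still holds at closure.

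**Working it through.** **Inputs from the documents.** 250 per group (Section 5); about 500 in total and about 100 per centre (Section 7). So 250 + 250 = 500, and 500 / 100 = 5 centres. No alpha, power, effect size or SD is stated, so the sample size cannot be reproduced.

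**Assumptions.** Two-sided 5%, normal data, and every SD, shift and offset below.

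**1. Signed rotation, equal means, SD 5° v 4°.** The standard error of the mean difference is √((25 + 16)/250) = 0.405°. The true difference is 0, so the t-test rejects at alpha, about 5%, whatever the SDs. Simulated Brown-Forsythe power is about 90%. At SD 6° v 3° the two figures are 5% and 100%; at 6° v 5°, 5% and 76%.

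**2. Signed rotation, SD 5° in both arms, mean shift 2°.** Standard error √(50/250) = 0.447°; 2/0.447 = 4.47; power ≈ Φ(4.47 − 1.96) = Φ(2.51) ≈ 99%. There is no gain in precision. Brown-Forsythe rejects about 5%.

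**3. Absolute rotation.** The mean of |X| for X with mean μ and SD σ is σ√(2/π)·exp(−μ²/2σ²) + μ(1 − 2Φ(−μ/σ)).

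| Group A (mean, SD) | Group B (mean, SD) | Mean abs. A | Mean abs. B | Power of t-test on absolute values |
|---|---|---|---|---|
| 0, 5 | 0, 4 | 3.99 | 3.19 | 91% |
| 0, 5 | 2, 4 | 3.99 | 3.58 | 35% |
| 0, 5 | 3, 4 | 3.99 | 4.05 | 6% |
| 2, 5 | 0, 4 | 4.30 | 3.19 | 99% |
| 3, 5 | 0, 4 | 4.69 | 3.19 | 100% |
| 0, 5 | 3, 5 | 3.99 | 4.69 | 67% (no gain in precision) |

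At equal means it does the job. Otherwise bias can hide a difference in spread, add to it or imitate one, depending on which arm is biased.

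**4. Is the sample large enough for a test of spread?** For an F-test of variances the upper critical value on 249 and 249 df is 1.283. Power reaches 80% at a variance ratio of 1.427, an SD ratio of 1/√1.427 = 0.84. Brown-Forsythe has about 72% power at 0.84 and 91% at 0.80. The approximate 95% CI for an SD ratio is the estimate times exp(±1.96·√(1/249)), that is × 0.88 to × 1.13.

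**5. What the Step 3 limit does by itself.** Assume SD 5° before adjustment. With p = 0.683 the probability of lying within one SD and φ(1) = 0.242:

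- If values are truncated at ±5°, SD = √(25(1 − 2 × 0.242/0.683)) = 2.70°.
- If values beyond ±5° are moved just to the limit, SD = √(25(0.683 − 0.484) + 25 × 0.317) = 3.59°.

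Against a Group A SD of 5°, Brown-Forsythe then rejects 100% or 97%. A narrower Group B at Step 3 is largely what the step is built to produce.

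**6. Pooled or centred test of spread.** Five centres with 50 per arm, one surgeon per centre assumed.

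- Surgeon offsets only in Group A, within-surgeon SD 5° in both arms: pooled Brown-Forsythe rejects about 18%, 43% and 80% at offset SD 2°, 3° and 5°. Centred within surgeon and arm, it rejects about 4–5%.
- Offsets shared by both arms, within-surgeon SD 6° v 5°: pooled 67% and 58% at offset SD 2° and 3°; centred 74% at both. With equal within-surgeon SDs (5°), both versions reject at about 5% or slightly below.

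Only the pooled version sees a reduction in differences between surgeons, which is part of total variability.

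**The case against.** Several points on the other side are sound.

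- **A rotation variable is named.** A reader might infer that the protocol has none. Step 3 gives CP Rotation a unit, a sign, a 5° target and an instruction to record it. Section 9 also refers to case report forms that are not among the documents and may define a field. What stands is that Sections 9 and 10 and Table 1 designate none as an outcome.
- **The family of tests is not in itself the defect.** Brown-Forsythe is an ANOVA on absolute deviations from the median, and a t-test on absolute rotation has the same power at equal means. The gap lies first in the undesignated variable and measure.
- **Absolute rotation is not useless.** A reader might infer so from the 35% and 6% figures, but those place the bias in the sensor-guided arm, which Step 3 steers towards alignment. With the bias in Group A, power is 99–100%. What stands is that it mixes bias with spread.
- **The difference in angle is weaker than the difference in stage.** Group A is read through a range of motion, Step 4 uses 10°, 45° and 90° for soft-tissue gaps, and Appendix I starts soft-tissue evaluation at 10°. A 10° value for Group A is probably obtainable.
- **A late Group B reading is plausible.** Figure 7 classifies a joint at closing, and Figure 4 shows loads and CP Rotation on one display. But no such rotation reading is stated.
- **Later change is unquantified.** A reader might infer that Group B's rotation drifts after Step 3. Appendix II lists a PCL release linked to contact-point position and recutting of the tibial plateau, so change is possible. The documents give no size for it.

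**Conclusion.** The point holds for Objective 1 and should be settled before data are examined. A precision objective has no designated outcome, no measure of spread and no test matched to it. On signed CP Rotation at 250 per arm, the named tests have about 5% power for an SD reduction from 5° to 4° at equal means, and about 99% power to declare a 2° shift that involves no gain in precision. The 5% follows from equal means and does not depend on the SDs; the other figures rest on assumed SDs and shifts and on normality.

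The mismatch in stage between the arms' stated readings is documented. Its effect is not quantified, and the documents do not support a claim that Group B loses its alignment after Step 3.

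Nor do they support two wider readings. The sample is not too small for this question, since an SD ratio of about 0.84 is within reach. Objective 2's clinical outcomes and safety are not affected.

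**What to change.** 1. **Designate one rotation outcome for Objective 1**, for example CP Rotation at 10° flexion. State how it relates to the software's tray rotation and to Group A's rotational alignment, and reconcile it with the tubercle wording of the objective.
2. **Pre-specify a comparison of spread before data are examined.** Main analysis: the SD ratio with a 95% CI and Brown-Forsythe on pooled values, which covers total variability including differences between surgeons. Supporting analysis: the same test centred within surgeon (or centre) and arm, to separate within-surgeon from between-surgeon spread. Also report the difference in the proportion within 5° and the mean signed difference, each with a 95% CI.
3. **Compare the arms at the same stage and angle.** Use, or record, a Group B value at 10° after balancing is complete and before arthrotomy closure, and extract Group A's 10° value from its existing reading. Keep the Step 3 value as a process measure. Hiding the display for the Group B reading is desirable only if it needs no added staff.
4. **If no matching late Group B value exists**, do not present Step 3 against Group A's closing value as evidence of precision. In any case, state as a limitation that Group B is judged by the sensor that guided it.

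**Cost.** A little analysis work and, where not already captured, one extra reading and case report form field in Group B, with a sensor already in use. This is a change of measurement and analysis only. The circularity in item 4 remains and can only be declared.
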